### **6.3 Demographic and Baseline/Screening Characteristics and Evaluations**

All demographic and baseline data will be summarized by descriptive statistics using the mITT population. The following variables will be presented:

#### **6.3.1 Demographics**

- Age (years)
- Sex (Female, Male)
- Ethnicity (Hispanic or Latino, Not Hispanic or Latino)
- Child Bearing Potentials (for females with childbearing potential only – Yes, No)
- Pregnancy Test Results (for females with childbearing potential only – Negative, Positive)
- Race (check all that apply: American Indian or Alaska Native; Asian; Black or Africa American; Native Hawaiian or Other Pacific Islander; White, Other. If Other, list of specified.)
- Blood Pressure – Systolic, Diastolic (mmHg)
- Iris Color (Black, Blue, Brown, Green, Grey, Hazel, Other. If Other, list of specified.)
- Central Corneal Thickness ( $\mu\text{m}$ )

#### **6.3.2 Medical History and Prior Ocular Procedures**

- Medical history by system organ class and preferred term
- Prior ocular procedures

#### **6.3.3 Ocular Hypertension and Glaucoma History**

- Type of glaucoma
- Glaucoma History

#### **6.3.4 Current IOP Lowering Medications**

- 

### **6.4 Protocol Deviations**

Number and percentage of protocol deviations will be summarized by the reason(s) for deviations.

Individuals subject listing of protocol deviation and reason(s) will be provided.

[figure not shown]
## 6.5 Efficacy Evaluation

Only **one** eye per subject will be included in the efficacy analysis.

If both eyes qualify for study inclusion, analyses will be provided for the worse eye at baseline. If both study eyes are the same at baseline, then data for only the right eye will be analyzed.

Efficacy analyses will be performed for the ITT, mITT and PP populations. Descriptive results will be presented for the overall group as well as for the Monotherapy and Concomitant Therapy groups.

[figure not shown]
There will be no statistical comparison between the Monotherapy and the Concomitant Therapy groups.

### 6.5.1 Primary Efficacy Variables

The primary efficacy variable is percent (%) reduction from baseline IOP.

### 6.5.2 Exploratory/Other Assessments

### 6.5.3 Sensitivity Analysis

Analyses on the primary efficacy outcome will be performed using the PP population.

## 6.6 Safety Analyses

The safety and tolerability of the study treatment will be determined by incidence and severity of treatment emergent AEs, clinical assessment of BCVA, IOP, eye examinations and biomicroscopy examinations.

All safety analysis will be based on the Safety population.

### 6.6.1 Adverse Events

All AEs reported during the study period reported for **both** eyes will be recorded and coded using MedDRA terminology and analyzed. An AE will be considered as treatment-emergent adverse event (TEAE) if it has an onset during the treatment period. A pre-existing event that worsens after the first dose date is considered a treatment emergent event.

The incidence of all TEAEs will be summarized using system organ class and preferred term. Adverse events will also be presented by relationship and severity. Further, serious adverse events and those events leading to discontinuation will also be presented.

Separate analyses will be performed for ocular and non-ocular TEAEs. For ocular TEAEs, the analytical unit will be eyes, and the total number of eyes in the safety population will be the denominator for incident rate of a specific ocular TEAE. For non-ocular TEAEs, subject will be the analytical unit and the number of subjects in the safety population will be the denominator for a specific non-ocular TEAE.

A subject/eye may have more than one AE per system organ class and preferred term. At each level of subject/eye summarization, a subject/eye will be counted once if 1 or more events were recorded and the highest severity will be reported. In cases where severity or relationship is missing, the most conservative approach will be taken (i.e. highest severity and assumed to be related).

The following summary tables of AEs will be presented:

- Adverse Events
  - Overall summary

- Ocular AEs
- By preferred term
- By preferred term and severity
- By frequency for SAEs
- By frequency for most common non-serious AEs

Most common non-serious AEs are any preferred term AE that at least 5% of the subjects report at least once.

- Treatment-Related AEs
  - Overall summary
  - By preferred term
  - By preferred term and severity
  - By preferred term and treatment session
  - Duration of AEs

The following overall summary will be presented:

- Total number and percentage of AEs
  - All AEs
  - Mild AEs
  - Moderate AEs
  - Severe AEs

Percentages for the total number of mild, moderate, and severe AEs will be based on the total number of all AEs.

- Total number and percent of subjects with
  - At least one AE
  - At least one SAE
  - No severe AEs but at least one moderate AE
  - No severe/moderate AEs but at least one mild AE
  - At least one AE leading to discontinuation

- Total number and percent of subjects with
  - All ocular-related AE
  - Mild ocular-related AE
  - Moderate ocular-related AE
  - Severe ocular-related AE
  - At least one ocular-related AE leading to discontinuation
  
- Total number of subjects who died (Treatment-emergent only)

Subject level listing will be provided with related information that include AE onset/resolution date, study days, duration, preferred terms, relationship to study treatment, action taken, outcome, and sorted by subject ID and onset date.

#### **6.6.2 Other Safety Assessments**

Frequency and percent of subjects/eyes with findings on visual acuity, blood pressure and biomicroscopy will be summarized for each visit.

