### 4.3.1 Inclusion Criteria

The following are criteria for inclusion in the study. Criteria required at the Baseline Visit (Visit 1, Day 0) ONLY are so indicated.

1. Male or female subjects (aged 18 or older)
2. Subjects diagnosed with open-angle glaucoma or ocular hypertension, and determined by the treating physician to require additional IOP-lowering treatment with netarsudil 0.02% either as first-line monotherapy, as a replacement of prior IOP-lowering medication, or used concomitantly with other IOP-lowering medication
3. Willingness to follow protocol requirements, including signed informed consent, routine follow-up schedule, completing questionnaires and completing laboratory tests

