### **11.3 Statistical Methods**

Summary tables (descriptive statistics and/or frequency distributions) will be provided for all baseline variables, efficacy variables, and safety variables. Continuous variables will be described by descriptive statistics (n, mean, standard deviation, range, and median). Frequency distributions (counts and percentage) of subjects within each category will be provided for categorical data. Additional analyses may be conducted as described in the Statistical Analysis Plan (SAP). The SAP will be finalized and approved prior to database lock.

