**11.3.3.2 Other Safety Assessments**

Other safety variables (as recorded on the eCRF) will be either summarized or listed based on the frequency.

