**APPENDIX 5: EXAMINATION PROCEDURES**

**1. Best Corrected Visual Acuity**

At all study visits, BCVA will be assessed in both eyes of each subject using a logarithmic visual acuity chart (Snellen or equivalent) at a distance of 12 feet.

Ensure subject is seated in a position whereby his/her eyes are 12 feet from the chart, which is hung on the wall at eye level. Mark a spot on the floor with a piece of tape to ensure subjects are seated in the exact same position every time they take the test. Also ensure subject is fitted with appropriate lenses as to provide “best correction” each time he/she takes the test. In order to standardize the conditions of the test as much as possible, all visual acuity testing should be performed in the same room under the same lighting conditions for every subject.

Perform the test on the right eye first. Ask the subject to read each letter, line by line, left to right beginning with line #1 on the top of the chart. Subjects should be told that the chart contains only letters, not numbers. If the subject reads a number, he/she should be instructed that the chart only contains letters and for him/her to “try again.” Subjects should be asked to read the letters slowly as to achieve best identification of each letter. There is no time limit for this test. Subjects are not to proceed to the next letter (or line) until they have given a finite answer.

If a subject changes a response (eg, that should be a “C” not an “O”) before he/she has read the next letter, the change will be accepted. If the subject attempts to change a response after reading the next letter in the series, the change will not be accepted.

When the letters become difficult to read or if the subject identifies a letter as 1 of 2 letters, he/she should be instructed to choose 1 letter and, if necessary, to guess. The examiner should consider the lowest line read with no more than 1 mistake as the extent of a subject’s visual acuity. This visual acuity should then be recorded (in Snellen equivalent units, eg, 20/80) on the appropriate CRF.

Repeat for the left eye.

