### **3.1.2 Safety Assessments**

- 1) Adverse Events**
- 2) Best-corrected Visual Acuity (BCVA)**

BCVA will be measured for both eyes by the investigator (or designee) at the Baseline Visit (Visit 1) and at both Visit 2 (Week 6) and Visit 3 (Week 12) using a Snellen Visual Acuity Chart (see protocol Appendix 5 for detailed information on this examination).

- 3) Biomicroscopy**

Biomicroscopy will be performed by the investigator (or designee) for both eyes at all visits by slit lamp examination without pupil dilation for the following locations:

- **Lids/Lashes (upper and lower)** – erythema, edema
- **Conjunctiva (Palpebral and Bulbar)** – Hyperemia, Edema, Follicles
- **Cornea** – Edema, Staining/Erosion
- **Anterior Chamber** – Cells, Flare
- **Lens Status** - Aphakic, Phakic, Pseudophakic, Not done. And if phakic, **Lens Appearance**

Observations for the slit lamp Biomicroscopy examination (except lens status) will be graded on a 5-point scale as follows (see protocol appendix 5 - Examination Procedures for detailed grading definition for each assessment):

- 0 = None
- 0.5 = Trace
- 1 = Mild
- 2 = Moderate
- 3 = Severe

- 4) Pregnancy Testing**

A urine human chorionic gonadotropin (hCG) pregnancy test (negative, positive). Only at Baseline Visit for females who are not diagnosed as postmenopausal or surgically sterile.

- 5) Blood Pressure (mmHg)**

At all visits. Systolic and Diastolic

- 6) Central Corneal Thickness (µm)**

Baseline only.

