## **6 STATISTICAL METHODS**

All data processing, summarization, and analyses will be performed using SAS® Version 9.4 or higher.

Unless otherwise specified, for continuous variables, descriptive statistics will include the number of subjects/eyes (n), mean, standard deviation, median, minimum and maximum values. Categorical variables will be summarized using frequency and percentages.

Unless, otherwise stated, missing data will be handled as is, except when the aforementioned dates are required for calculations, the partial dates will have either '01' or 'Jan' imputed with an exception for dates related to AEs where the date closest to the last event (visit date, etc.) should be used rather than arbitrary '01' of that month.

All efficacy data will be summarized at each time point using appropriate descriptive statistics. Summaries will be presented for the ITT, mITT and PP populations. All summaries and analyses will be performed using data pooled across centers.

Baseline assessment will be those recorded prior to dosing. In cases where more than one pre-dose observation has been recorded, the **last recording** will be identified as the baseline assessment.

Study days will be numbered relative to the study starting date (Visit 1, presumably, the first dosing date).

Recorded data will be assigned to evaluation/assessment windows. If more than one clinical evaluation is made within a window for a particular visit, the record with the date closest to the targeted window will be used except for AEs where the **worst assessment** will be used.

Visit windows and analytical windows are defined as follow:

Visit	Targeted Window	Analytical Window
Visit 1 (Baseline, First dosing date)	Day 0	Day 0
Visit 2	Week 6 ( $\pm$ 7 day)	Day 2 to Day 63
Visit 3 (End of treatment visit)	Week 12 ( $\pm$ 7 days)	Day 64 to End of Study

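### By-visit summaries of visual acuity, biomicroscopy and blood pressure are not paired with each eye's or subject's own baseline, so they do not identify new or worsened findings

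*SAP*

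**What the plan says.** SAP 6.6.2 is a single sentence: "Frequency and percent of subjects/eyes with findings on visual acuity, blood pressure and biomicroscopy will be summarized for each visit". Protocol 11.3.3.2 is no more specific: "Other safety variables (as recorded on the eCRF) will be either summarized or listed based on the frequency". Neither document defines a finding for any of the three assessments. SAP 7.3 mentions potentially clinically important vital signs but gives no criteria.

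The data are richer than a yes/no finding. On biomicroscopy, SAP 3.1.2 says: "Observations for the slit lamp Biomicroscopy examination (except lens status) will be graded on a 5-point scale as follows", with grades 0, 0.5, 1, 2 and 3. On acuity, Protocol Appendix 5 says: "This visual acuity should then be recorded (in Snellen equivalent units, eg, 20/80) on the appropriate CRF". Blood pressure is recorded in mmHg. Protocol Appendix 4 schedules all three at baseline, Week 6 and Week 12, and SAP 4.5 names all three as safety endpoints.

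Two general rules also apply. Protocol 11.3 says: "Summary tables (descriptive statistics and/or frequency distributions) will be provided for all baseline variables, efficacy variables, and safety variables", and goes on to promise counts and percentages by category for categorical data. SAP 6 says: "Unless otherwise specified, for continuous variables, descriptive statistics will include the number of subjects/eyes (n), mean, standard deviation, median, minimum and maximum values". SAP 6 also defines baseline: "Baseline assessment will be those recorded prior to dosing". No section uses that definition to form a change, shift or worsening category for these assessments.

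**The concern.** SAP 3 describes a single-arm study. With no concurrent control, the eye's or subject's own pre-dose value is the only internal reference for judging whether a sign, an acuity loss or a blood-pressure change arose on treatment.

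Findings before the first dose are possible by design. Besides first-line use, Protocol 4.3.1 admits subjects who receive netarsudil "as a replacement of prior IOP-lowering medication, or used concomitantly with other IOP-lowering medication", and Protocol 5.1.4 requires no washout on replacement. Lens opacity is itself one of the graded signs. A percentage at each visit mixes pre-existing findings with new ones, and new findings can be offset by resolved ones.

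Two further SAP rules bear on who and what is counted. SAP 6.2.3 does not map the safety assessment at treatment-discontinuation exit to a visit, and treats it as the final on-treatment assessment. SAP 6.6.2 has by-visit summaries and no row for a last or worst assessment. SAP 6 resolves several records in one window by taking the one nearest the target, and reserves the worst-record rule for adverse events. A worse slit-lamp grade at an unscheduled visit can therefore be passed over.

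**Working it through.** The plan gives no figure on this point, so there is nothing to reproduce. The check has four steps.

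**1. What visit percentages identify.** Let p0 and p12 be the proportions of eyes with a finding at baseline and Week 12, and r the proportion with it at both.

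- New onset = p12 − r.
- r lies between max(0, p0 + p12 − 1) and min(p0, p12).
- New onset therefore lies between max(0, p12 − p0) and min(p12, 1 − p0).

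Inputs: about 250 subjects (Protocol 11.1) with both eyes evaluated (SAP 3), so 2 × 250 = 500 eyes. The documents give no finding rates, so every p0 and p12 below is an assumption. The same 500 eyes are taken to be seen at both visits.

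For 30% and 45%, r lies between 0 and 0.30. New onset lies between 0.45 − 0.30 = 0.15 and 0.45 − 0 = 0.45, which is 75 to 225 eyes.

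| Baseline | Week 12 | New onset, % of eyes | New onset, eyes of 500 | Most eyes affected at both visits |
|---|---|---|---|---|
| 5% | 5% | 0 to 5 | 0 to 25 | 25 |
| 20% | 20% | 0 to 20 | 0 to 100 | 100 |
| 20% | 30% | 10 to 30 | 50 to 150 | 100 |
| 40% | 40% | 0 to 40 | 0 to 200 | 200 |
| 30% | 45% | 15 to 45 | 75 to 225 | 150 |

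The last column, min(p0, p12) × 500, is the largest number of eyes that could have changed grade without altering a present/absent percentage.

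**2. Whether grade distributions close the gap.** They help but do not close it. If five-level distributions are shown at each visit, a net movement from trace to severe is visible. The bounds in step 1 do not change, because they depend only on the none-versus-any margin and any split into grades is compatible with them. Upward and downward moves still cancel: at 20% and 20% with identical grade splits, anywhere from 0 to 100 eyes could be newly affected.

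**3. Blood pressure.** In subjects seen at both visits, mean change equals the difference in visit means, so the mean is recoverable. The spread is not. SD of change = √(s0² + s12² − 2ρ·s0·s12). With equal SDs s this is s√(2(1 − ρ)), which is 0 at ρ = 1 and √2·s = 1.41s at ρ = 0. Visit SDs do not give ρ and do not show which subjects changed most. If some subjects leave, the visit means also come from different people.

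**4. Exit assessments.** Under SAP 6.2.3 the efficacy value at exit goes to the next scheduled visit, but the safety value does not. SAP 6.6.2 summarises by scheduled visit. Set side by side, the two sections give the exit safety value no stated row. Adverse events are a listed reason for leaving (Protocol 9.2), so a Week 12 percentage could fall because affected subjects had gone.

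**The case against.** The strongest case on the other side has four parts.

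- **Grades need not be lost.** A reader might infer that 6.6.2 collapses every sign to present or absent, so that trace-to-severe hyperaemia leaves the table unchanged. The documents do not say so. Protocol 11.3 promises counts by category for safety variables, SAP 6 repeats this for categorical variables, and SAP 1.1 declares no change from the protocol. Grade distributions and blood-pressure means by visit are a fair reading. This objection stands, but those summaries remain margins (steps 2 and 3).
- **Treatment-emergent worsening is analysed elsewhere.** A reader might infer that the plan yields no such information. It does. An adverse event includes a sign that appears or worsens and can be elicited on examination (Protocol 10.1, SAP 3.7). A worsened pre-existing event counts as treatment-emergent, and ocular events are analysed per eye (SAP 6.6.1). This also stands. Its limit is that no rule says what change in grade, acuity line or mmHg must be reported as an adverse event.
- **Listings and unseen shells.** Subject listings (SAP 7.4) allow comparison by hand, and SAP Module II, which holds the table shells, was not available. Paired tables may exist there. If so, 6.6.2 should name them, because Module I states the methods.
- **The data are not uniform.** Blood pressure is per subject. Lens appearance is graded in phakic eyes only. Appendix 5 reserves fluorescein for suspected erosion, while the staining grades are defined by it. The fix has to respect this.

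Two further inferences would go too far. Eligibility shows that subjects may enter on other drops, but no proportion is given, so it cannot be said that many do. And the exit assessments are not said to be dropped; their place is unstated.

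**Conclusion.** The point holds in this form: as written, the SAP 6.6.2 tables do not pair an eye or subject with its own baseline, so they do not identify new or worsened findings on acuity, biomicroscopy or blood pressure. Adding grade distributions and means by visit would not change that. The point does not extend to the TEAE tables, which count worsening when it is reported as an adverse event.

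The size cannot be taken from the documents. Under the assumed 30% and 45%, new onset could be anything from 15% to 45% of eyes. Other assumed rates give ranges from 0 to 25 eyes (5% at both visits) up to 0 to 200 eyes (40% at both). These show how little the margins determine and are not predictions.

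Primary efficacy, sample size and error rates are unaffected. The change is still worth making, because these are named safety endpoints in a study with no control arm. The conclusion rests on the protocol and SAP Module I only.

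**What to change.** In SAP 6.6.2, define a finding for each assessment, keep the by-visit summaries and add:

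- **Biomicroscopy.** Per-eye shift tables for each graded sign, from baseline to Week 6, Week 12 and the worst or last on-treatment assessment, with exit assessments included in the latter. Restrict lens appearance to phakic eyes and corneal staining to eyes examined with fluorescein. The documents do not show whether fluorescein use is recorded on the CRF; if it is not, list staining rather than tabulate shifts.
- **BCVA.** Per-eye change from baseline in lines or logMAR, with the percent of eyes worsening by a prespecified number of lines.
- **Blood pressure.** Within-subject change from baseline in systolic and diastolic pressure, with SD.

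Use as denominator the eyes or subjects with both a baseline and the relevant later value. State where exit assessments appear, and that the worst on-treatment column draws on all records rather than only the one nearest the target day.

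The cost is SAP wording, a few more tables and their programming. No new data are needed, since all three assessments are already scheduled at baseline, Week 6 and Week 12.

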## **7 CONVENTIONS AND ALGORITHMS**

### **7.1 Decimal Points**

All summary tables involving percentages will round the percentages off to 1 decimal place.

All summary tables involving descriptive statistics of continuous variables will round the mean and median to 1 decimal place more than the variable's standard form and round the standard deviation to 2 decimal places more than the variable's standard form. The standard form of a percent change variable is 0 decimal places.

### **7.2 Study Days**

Study days will be computed for each visit and AE event.

$$\text{Study Days} = \text{Date of Visit/Event} - \text{Date of First Dose} + 1$$

Or, if the visit/event occurs prior to the Day 1

$$\text{Study Days} = \text{Date of Visit/Event} - \text{Date of First Dose}$$

Date of First Dose is the Day 1 Visit date.

Last Date in study is the Day 84 Visit or the last visit where the subject was seen by the investigator. If lost-to-follow-up, the last date of contact is the Last Date in study.

If a subject had contact with the site after the final visit (e.g. for AE follow up), the last visit date will be the Last Date in study, not the contact date.

Time in Study (Study duration) = Last Date in study – Date of First Dose + 1

Time in Study Treatment (Treatment duration) = Date of Last Dose – Date of First Dose + 1

### 7.3 Multiple Occurrence of Events

When summarizing AEs, potentially clinically important laboratory findings, potentially clinically important vital signs, and subjects with multiple occurrences of an event will be counted only once in the summary. When AEs are summarized by severity, if the subject has multiple occurrences of the same AE, the most severe will be used for the summary.

When summarizing concomitant medications by drug class and by preferred term, if two medications are coded to the same preferred term, both will be counted for a subject.

